The Timed up and Go (TUG) test measures time acquired to walk three meters back and forth as fast as possible although running is not allowed. The subject starts from a sitting position in an armchair (seat height approximately 43-47 cm) and asked to rise from the chair on an “three, two, one, go” start-signal and walk three meters, then turn around at the mark on the floor, and walk back to the chair and sit down again. Time is measured from the “go” signal and stopped when the subject again is positioned in the chair using the back rest. All subjects are asked to wear supporting shoes and subjects not using such shoes are asked to perform the test barefooted.

The Chair Stand Test (CST) assesses lower body strength and power through the ability to rise from a chair and sit back down. Test subjects are required to stand up from a standard chair to a fully extended standing position with their arms folded across their chest. From the sitting position, the subject stands completely up, then completely back down, and this is repeated for 30 seconds. The total number of complete chair stands (up and down equals one stand) is counted.

Usual gait speed (UGS) takes place over 6 meters and composites of 4 meters of measuring, 1 meter of acceleration and 1 meter of deceleration. Subjects must walk at their own pace. Time <0,8 m/s (5 seconds on 4 meters), is viewed as cut off.

Estimated time: 5-10 min.

Assessments of OCT, Fundus and Visual Examination

All subjects will be tested with Optical Coherence Tomography (OCT), fundus photo and visual examination. Eyes will not be dripped. OCT is a non-invasive scan of the retina to measure the size and layer in combination with a fundus photo of the retina to assess the visual nerve and macula. If the subjects recently have been scanned at Aalborg University Hospital within 3 months, there is no need of a new one in case of stable eye-condition. The eye department at Aalborg University Hospital will assess the pictures.

Estimated time: 30 min.

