4.2. Study population

The study strives to include a total of 300 subjects with T2D divided into three well-defined groups:

- T2D F-/N-: Subjects with T2D and no previous history of any fractures or diabetic neuropathy ($n=160$)
- T2D F+: Subjects with T2D with a previous history of a fracture(s) (any fracture, major osteoporotic fracture (MOF) and peripheral) ($n=100$)
- T2D N+: Subjects with T2D matched by age and sex with severe peripheral (vibration perception threshold (VPT) > 50) or a history of autonomic neuropathy ($n=40$).

[figure not shown]

Figure 2: Study design

Inclusion criteria

1. Men and women with minimum 40 years of age.
2. Diagnosis of T2D. At least one of the following criteria must be met at diagnosis:
 - a. HbA1c ≥ 48 mmol/mol (6,5 %)
 - b. Plasma glucose $\geq 11,1$ mmol/l
 - c. Fasting plasma glucose $\geq 7,0$ mmol/l
3. Clinical effect of oral antidiabetic medication strengthens the diagnosis.
4. Diagnosis of diabetes at least one year prior to inclusion of the study.
5. A history of fracture(s) (confirmed by radiographs analyzed by radiologist) following the diabetes diagnosis (T2D F+ group)
6. Diagnosed with severe peripheral (VPT ≥ 50) or autonomic neuropathy defined by cardiac autonomic reflex tests or severe abnormalities in orthostatic blood pressure (T2D N+ group)
7. Signed the informed consent.
8. Not defined by the exclusion criteria.

Exclusion criteria

1. Severe decreased liver function (Alanin amino-transaminase (ALAT) >250 U/l, Gamma-Glutamyltransferase (GGT) >150 U/l).
2. Moderate to severe kidney dysfunction, estimated Glomerular Filtration Rate (eGFR) <15 mmol/L/1,73m².
3. Pregnancy or breast feeding.
4. Active malignancy or terminal ill.

5. Previous chemotherapy or immunomodulating treatment
6. Known severe vitamin deficiency
7. Current or previous alcohol- or drug abuse.
8. Not being able to understand Danish written and/or verbally.
9. Terms according to investigators judgement that makes subjects unsuitable to participate including lack of ability to understand and comply with instructions and/or reduced physical ability, limiting the ability to participate in the examinations.
10. Participating in other clinical studies utilizing experimental treatment or medication.
11. Subjects with pathologic fractures (defined as fractures due to local tumors, tumor-like lesions, or focal demineralization as visualized on radiographs).

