Perception Threshold Tracking (PTT)

Perception Threshold Tracking is a potential new method for early detection of neuropathy. It is a further development of conventional threshold tracking that excels in describing membrane potential of not only large, but also small nerve fibers. The trial is conducted using two types of surface electrodes placed on the dorsum of the foot: patch and pin electrodes for stimulation of large and small nerve fibers respectively. The perception threshold is then estimated by slowly increasing the intensity of stimuli until the subject presses a button indicating that the stimuli is perceived. As this happens, the intensity is initially heightened by 20 % and then lowered until the subject relieves the button indicating that the stimulus is no longer felt. The intensity is then lowered by 20% and then increased until perception is indicated by pressing the button. This is repeated three to five times to increase precision. The perception threshold is taken as the average of the six to ten times the subject pressed the button. This procedure will be repeated several times using different electrodes. The subject will feel no significant pain, as the stimuli given is just around the individual perception threshold, which is a huge benefit of this method compared to other available neural tests. There will be no risk of burns or injury to the skin, as the stimulator is limited to supplying electricity well below any dangerous level.

Estimated time: 10-15 min.

NC-stat DPNCheck

Gel is applied to the apparatus and the one-time electrode is connected. The device is then placed following the sural nerve from just behind the malleus and up the back of the leg. Using a short electrical stimulation, the device records the nerve conduction velocity and amplitude.

Estimated time: 5 min.

Skin biopsy

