Skin biopsy will be performed on the 40 subjects in the T2D N+ group, 40 subjects in the T2D F+ group and 40 subjects in the T2D F-/N- group. After ensuring sufficient blood flow the skin is anesthetized using 0,5-1 ml Lidocaine. After 3-5 minutes it is ensured that the skin is indeed numb. After confirming this, two punch biopsies are taken just above the ankle. The biopsies will be taken using a disposable 3-mm punch under usual sterile conditions. Potential bleeding is stopped by compression and the wound is bandaged as per normal clinical procedure. Before the subject leaves, it is ensured that the bleeding has stopped. Participants are informed to keep the wound dry for 2 days and to change the bandages if needed. Skin biopsies will not be taken if the participant has skin diseases in the biopsy area or has any known hematologic disorders resulting in markedly reduced ability to stop small bleedings.

Skin biopsies will be analyzed at the Danish Pain Research Center, Aarhus University. Sections will be stained using the free-floating protocol, and IENF quantified following available guidelines. Additionally, regenerative-related antibodies will be used to identify potential biomarkers of early onset neuropathy. The antibodies used will include but are not limited to PGP and GAP-43.

Estimated time: 15-20 min.

Quantitative Sensory Testing

Quantitative Sensory Testing (QST) is a way of assessing large and small sensory nerve fiber function using several different stimuli. The method has been verified using different protocols, and will be conducted in accordance with the original protocol by German Research Network on Neuropathic Pain (DFNS)⁷⁸. All measurements are made on the dorsum of the foot. The protocol consists of seven tests measuring 13 parameters including, but in this study, we will only assess thermal detection. The tests will be performed using a thermal sensory testing device. Cold detection threshold (CDT) and warm detection threshold (WDT) are measured and calculated as a mean of three consecutive measurements. The thresholds are to be obtained with ramped stimuli increasing by 1 degree Celsius per second, terminated as the subject presses a button. Cut-off temperatures are set at 14 and 50 degrees Celsius, and the baseline temperature is set at 32 degrees Celsius, as this represents the mean value of skin temperature.

Estimated time: 10 min

Vagus Test Procedure

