6.4. Missing data

Missing data, interpretation errors, coagulation defects are considered missing values and will not be included in the analysis. In this case, each sample requisition is numbered (N). Furthermore, samples that cannot be measured in numerical values are categorized as missing values.

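### A person who feels nothing at the stimulator's limit has no PTT value, and one without a sural response has no conduction velocity; section 6.4 then excludes the most severe results on these two measures

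*Protocol*

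**What the plan says.** Section 4.5 of the protocol (Perception Threshold Tracking) describes the procedure thus: "The perception threshold is then estimated by slowly increasing the intensity of stimuli until the subject presses a button". The value is then formed as follows: "The perception threshold is taken as the average of the six to ten times the subject pressed the button". The same paragraph states that "the stimulator is limited to supplying electricity well below any dangerous level". It gives no maximum output and no result for someone who never presses.

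For NC-stat DPNCheck on the sural nerve, section 4.5 says that "the device records the nerve conduction velocity and amplitude". It has no rule for an absent response.

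For thermal testing, section 4.5 does fix limits: "Cut-off temperatures are set at 14 and 50 degrees Celsius". It does not add that a threshold not felt is scored at the limit.

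Section 6.4 says: "Missing data, interpretation errors, coagulation defects are considered missing values and will not be included in the analysis".

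Section 4.2 plans 40 people in N+ and 160 in F-/N-. Inclusion criterion 6 for N+ reads "Diagnosed with severe peripheral (VPT ≥ 50) or autonomic neuropathy", the latter established by cardiac reflex tests or orthostatic blood pressure.

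**The concern.** A test that needs a response gives no number when there is none. If that blank is handled as ordinary missing data, values are lost because of how severe the neuropathy is, not at random. The loss falls on the part of the scale that N+ was recruited to fill.

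Two uses of the data are exposed. A comparison of PTT threshold or sural velocity between N+ and F-/N- would rest on the milder part of N+. A regression of bone or balance measures on either variable, as might be done under the second aim in section 3, would lack its severe end. The fifth aim, which takes neuropathy as an outcome, is open to the same loss wherever these two measures are used.

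This goes beyond detail that a statistical analysis plan would normally supply, for two reasons. The protocol itself fixes exclusion as the rule. And if a no-response is not recorded apart from a technical failure or a refusal when the test is done, no later plan can recover it.

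**Working it through.** **Tracing the two measures**

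- PTT: the value is a mean of presses. With no press up to the output cap there is nothing to average, no substitute is stated, and the general missing-data sentence of section 6.4 applies.
- Sural nerve: with no response, velocity cannot be computed. Amplitude could be entered as 0, which is a number. Only velocity is certain to be lost.
- Thermal thresholds: numerical limits exist, so a natural value is available. The text needs only to confirm its use.

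**Size of the distortion**

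The protocol has no figure of its own to reproduce here: it gives neither a no-response rate nor a maximum output. What follows is an illustration on assumed values.

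Inputs from section 4.2: N+ 40, F-/N- 160. Assumptions: the underlying threshold is normal with SD 1 in both groups; the mean is 0 in F-/N- and D in N+; one common limit c applies; a share f of N+ lies above it.

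With φ and Φ the standard normal density and distribution function:

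- limit: c = D + k, where k = Φ⁻¹(1 − f)
- mean of N+ after exclusion: D − φ(k)/Φ(k)
- mean of F-/N- after exclusion: −φ(c)/Φ(c)
- observed difference: D − φ(k)/Φ(k) + φ(c)/Φ(c)

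Worked case, D = 1.0 and f = 10%: k = 1.282 and c = 2.282, so φ(k)/Φ(k) = 0.1755/0.90 = 0.195 and φ(c)/Φ(c) = 0.030. The observed difference is 1.0 − 0.195 + 0.030 = 0.835, a loss of about 17%.

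| True difference (SD) | N+ off scale | N+ left of 40 | Difference after exclusion | Loss | Difference if scored at the limit |
|---|---|---|---|---|---|
| 1.0 | 10% | 36 | 0.83 | 17% | 0.96 |
| 1.0 | 25% | 30 | 0.68 | 32% | 0.87 |
| 1.0 | 50% | 20 | 0.49 | 51% | 0.68 |
| 1.5 | 10% | 36 | 1.31 | 12% | 1.45 |
| 1.5 | 25% | 30 | 1.11 | 26% | 1.36 |
| 1.5 | 50% | 20 | 0.84 | 44% | 1.13 |

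(Losses are computed from unrounded differences.)

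The direction is the same in every row. Scoring at the limit recovers much of the loss but not all of it, because values beyond the limit are still compressed.

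At a smaller true difference of 0.5 SD the relative loss is larger. The observed difference is 0.39, 0.30 and 0.21 SD at 10%, 25% and 50% off scale, and power for 160 versus 40 at two-sided 5% falls from 0.81 to 0.69, 0.52 and 0.29. At 1.0 SD or more, power stays at 0.90 or above, so the problem there is bias rather than power.

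**The case against.** The strongest reply is that no sentence in the protocol says a no-response is discarded. That reading joins silence in section 4.5 to section 6.4, and much of section 6.4 is laboratory language (coagulation, requisitions, samples without a numerical value). This stands for the sentence on samples, which may concern laboratory material only, so the point does not rely on it. It does not answer the general sentence on missing data: a PTT field with no presses is blank, and blank values are excluded.

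Several stronger readings are tempting, and the protocol does not support them:

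- A reader might infer that people drop out of the study or that neuropathy is understated throughout. N+ membership rests on vibration threshold, cardiac reflex tests or orthostatic pressure, not on PTT or DPNCheck. All 40 stay in the bone comparisons, and biothesiometry, Vagus, COMPASS-31, MNSI and skin biopsy are separate measures.
- A reader might infer that much of N+ will be off scale. No rate is given, and N+ can be entered through autonomic neuropathy alone. Low rates are as admissible as high ones.
- A reader might include thermal testing as equally affected. It has stated numerical cut-offs and follows a cited method, so one confirming sentence is enough.
- A reader might say that the sural test yields nothing at all. Amplitude can be 0.

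It can also be said that the choice of model belongs in an analysis plan. That is fair: section 6.2 already allows non-parametric methods, so a censored model is one option among several.

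**Conclusion.** The point holds for the PTT threshold and for sural conduction velocity. As written, the plan leaves a no-response on either without a value and excludes missing values, so the worst results are lost and analyses of these two measures lean towards less neuropathy.

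The size depends on a rate that the protocol does not give. Under normal distributions with equal SD, a common limit and a true difference of 1.0 to 1.5 SD, the observed N+ versus F-/N- difference shrinks by about 12 to 17% with 10% of N+ off scale and by about 44 to 51% with 50% off scale. If no-responses prove rare, the effect is small.

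The change should be made because the bias has a known direction and the remedy is nearly free, provided that it is in place when the tests are recorded.

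**What to change.** In section 4.5:

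- State the maximum PTT output, and record a PTT no-response as censored at that value.
- Record an absent sural response as amplitude 0 with velocity not obtainable.
- Flag both apart from technical failure and refusal.
- Confirm that a thermal threshold not felt is scored at the stated cut-off.

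In section 6.4, exempt these results from exclusion.

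Analyse them by ranks, which section 6.2 already permits, or by an ordinal or censored model, with no-response as the worst value. Report the number of no-responses by group for each test.

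Cost: a few sentences, one flag per test in the case report form, and a rank, ordinal or censored analysis in place of a t-test for these measures. No new measurement is needed.

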A commercially available handheld device (Vagus™, Medicus Engineering Aps, Aarhus N, Denmark) will be used to test the autonomic nervous system and hereby the autonomic neuropathy. The participant will hold the device during four steps, where the device will 1) measure the heart rate at rest, 2) measure the heart rate response from laying position to standing position, 3) measure the relationship between heart rate during expiration and inspiration, and 4) measure the heart rate conditions during exhalation with a

resistance of 40mmHg and at rest. The latter will not be performed if the subject has known proliferative diabetic retinopathy or other known diseases with risk of retinal bleeding. The test is defined as abnormal if Cardiac Autonomic Neuropathy (CAN)-Score is ≥ 2 .

Estimated time: 15-20 min.

COMPASS-31

A questionnaire about symptoms of autonomic neuropathy (attached). Gives us the opportunity to measure non-invasive and stratify people with and without neuropathy. Will be filled on iPad by the participants, and entries are transferred to REDCap.

Estimated time: 10 min.

Michigan Neuropathy Screening Instrument (MNSI)

MNSI (attached) will be used as a part of the screening process for diabetic neuropathy. MNSI includes two separate assessments: a 15-item self-administered questionnaire (filled in REDCap by the participants) and a lower extremity examination that includes inspection and assessment of vibratory sensation and ankle reflexes. Estimated time: 15 min.

Assessment of muscle strength

Isometric handgrip strength will be assessed by a hand dynamometer (NC70144, Procare.dk, Denmark). Each subject is instructed to exert maximal contraction force with their dominant hand (defined as their “writing hand”), when standing in an upright position and the hand tested pointing downwards, parallel to the body, and unsupported. Each subject repeats the test three times. The maximal contraction level of the three trials is selected for further analysis.

Isometric measurement of knee extension strength will be measured with hand-held dynamometer. Similar procedures as for the arms.

Estimated time: 5 min.

Test for postural control

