9.1. Informed consent

Subjects interested in participating in the study will receive written information about the project ("Dine rettigheder som forsøgsperson i et sundhedsvidenskabelig forskningsprojekt" produced by *Den National Videnskabsetiske Komité (NVK)*) and a folder of the study ("deltagerinformation"). If the subject is interested in participating in the project after reading the written information, they will be asked permission to access medical records for screening in accordance with the Danish law. Medical records will be assessed for information on comorbidities and diabetes complications, relevant diagnostic imaging, medications, and previous biochemistry to ensure the potential participant is suitable for inclusion. If suitable for inclusion after screening medical records, they will be invited for a personal meeting, where all details for the study will be outlined by the investigator or a delegated assistant. The subject will be informed about the opportunity to bring a lay representative in advance of the meeting. The meeting will take place in a closed room without any disturbances, e.g. phone calls. Subjects will be invited for an additional visit at our center to sign the informed consent (IC) form and further screening. After signing the IC, the subject will have blood samples taken for screening. Furthermore, we will assess status of neuropathy with questionnaires and physical examination including biothesiometry, NC-stat-DPNCheck, orthostatic blood pressure and Vagus test, and the subjects will receive equipment and instruction for the 24-hour urine sample to collect before the study day.

The subjects must be fully informed of their rights and responsibilities while participating in the trial as well as possible disadvantages of potential risks. The investigator must ensure the subject has ample time to come to a decision whether to participate in the trial. A voluntary, signed, and personal dated IC must be obtained from the subject before any trial-related activity. The responsibility for seeking IC must remain with the investigator, but the task may be delegated by the investigator to a medically qualified person, in accordance with local requirements. The IC must be signed and personally dated by the person who seeks the IC before any trial-related activity. Subjects will be informed that information given in relation to the project before signing the IC will be passed on to the investigator.

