- **DXA and HR-pQCT:** The risks of adverse reactions from the DXA or the HR-pQCT scans are minimal due to the low dose of radiation applied through the test. In theory this will increase the life-time risk of cancer from approximately 25% to less than 25,00002 %. No children or pregnant women are included in the project. The DXA scan may show sign of osteoporosis, which is an asymptomatic condition, mostly diagnosed after a fracture have occurred. Thus, it will be an advantage for subjects to have this diagnose assessed prior to any fracture occurrence. If osteoporosis is diagnosed, they will be referred to their general practitioner for further assessment and treatment.
- **Microindentation:** Participants will experience slight discomfort from microindentation due to localized pain in relation to the insertion site and, rarely, hematoma. Complications such as hematoma from microindentation are rare. There is a small risk of infection and reaction to local anesthesia such as redness, itching and subcutaneous hematomas. **PTT:** Participants might feel a small amount of transient pain during the examination. No lasting pain will occur.

- **Skin biopsy:** Participants might feel a small amount of transient pain during and a small bleeding. No lasting pain will occur. There is a small risk of infection and reaction to local anesthesia such as redness, itching and subcutaneous hematomas.
- **OCT, Fundus Photography and visual examination:** It is a common procedure performed by trained personnel. Eyes will not be dripped.
- **Vital signs and body measurements, 12-lead ECG, skin AGE Reader, Vagus™, QST, NC-stat DPNCheck, force platform, gait function and muscle strength assessments:** No risks or side-effects.

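### Section 9.2 lists the Vagus test as free of risk although section 4.5 withholds one of its steps for retinal bleeding risk, and the protocol does not say how retinal status is established before that step

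*Protocol*

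**What the plan says.** Section 4.5 (Vagus Test Procedure) describes a handheld autonomic test in four steps. The last is exhalation against a "resistance of 40mmHg and at rest". For that step it adds: "The latter will not be performed if the subject has known proliferative diabetic retinopathy or other known diseases with risk of retinal bleeding".

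Section 9.1 describes the order of events. Medical records are reviewed first, including diabetes complications and relevant imaging. A personal information meeting follows, and then: "Subjects will be invited for an additional visit at our center to sign the informed consent (IC) form and further screening". At that visit neuropathy is assessed by questionnaires and an examination that includes "biothesiometry, NC-stat-DPNCheck, orthostatic blood pressure and Vagus test". The visit comes before the study day, because subjects leave with "instruction for the 24-hour urine sample to collect before the study day".

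Section 4.5 (Assessments of OCT, Fundus and Visual Examination) states: "All subjects will be tested with Optical Coherence Tomography (OCT), fundus photo and visual examination". It gives one exception: "If the subjects recently have been scanned at Aalborg University Hospital within 3 months, there is no need of a new one", provided the eye condition is stable. No visit is named.

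Section 9.2 goes through the examinations and gives the risks of each. Its last entry, which begins "Vital signs and body measurements, 12-lead ECG, skin AGE Reader, Vagus™, QST, NC-stat DPNCheck", declares everything it lists to be without risks or side effects.

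**The concern.** There are two linked problems.

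First, the protocol recognises a hazard in one section and denies it in another. Section 9.2 is where the protocol sets out risks by examination, and a retinal risk that the sponsor took seriously enough to restrict a procedure does not appear there. Anyone relying on 9.2 for the risk assessment would be misled.

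Second, the restriction protects only people whose retinal disease is already on record. If the study's own retinal imaging comes after the Vagus test, that imaging cannot inform the decision to do the resisted exhalation. A participant with undocumented proliferative retinopathy would then perform a step that the protocol withholds from anyone known to have the condition.

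**Working it through.** No arithmetic applies: the point depends on no rate, effect size or sample size. The check is a side-by-side reading.

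1. **Does the protocol treat the step as hazardous?** Yes. Section 4.5 removes only the resisted exhalation, and only for people with proliferative retinopathy or another disease that carries a retinal bleeding risk. The restriction has no other evident purpose.

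2. **Does section 9.2 disclose this?** No. The Vagus test is in the group declared free of risk. Elsewhere the same list mentions quite minor matters: near-negligible infection risk from blood sampling, rare haematoma after microindentation, brief pain during perception threshold tracking. The omission therefore cannot be put down to a list confined to serious risks.

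3. **When is the Vagus test done?** At the consent and screening visit (section 9.1), before the study day.

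4. **What is known about the retina by then?** Whatever the records review finds. Section 9.1 does not require an eye result to be present or recent. As written, a subject with no eye result on file counts as not known to have disease, and the step goes ahead.

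5. **Are people with retinopathy kept out of the study?** No. None of the exclusion criteria in section 4.2 concerns retinopathy, and section 3 names retinopathy among the microvascular complications to be studied.

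6. **When is the retina imaged?** The screening procedures in section 9.1 include no OCT, fundus photo or visual examination. Section 4.5 gives these to all subjects without naming a visit. The natural reading is that they come after screening, but this is an inference. The inclusion flowchart announced in section 14 is not shown and might settle it. A subject with a stable eye condition and a hospital scan in the previous 3 months needs no new scan, so for those subjects imaging precedes the Vagus test.

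Result: the conflict between 4.5 and 9.2 is certain. That the safeguard depends on prior knowledge, with no eye result required, is also certain. The order of Vagus test and study imaging is inferred.

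**The case against.** The strongest reply is that section 9.2 describes the risk left over after section 4.5 has removed people with recognised disease, so the two agree. This would hold if the restriction caught everyone at risk. It catches only known disease, and no eye result is required beforehand, so section 9.2 cannot claim that nothing remains.

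A second reply is that the records are reviewed before any visit and that the protocol uses the same *known* standard elsewhere, for example for peripheral arterial disease and lidocaine allergy. The review does narrow the gap. It does not close it, because it sets no minimum for eye information.

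Several stronger readings are tempting but not supported:

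- A reader might infer that the Vagus test is definitely done before the fundus photo. The protocol names no visit for the imaging, so this remains an inference.
- A reader might infer that participants are told in writing that the test has no risk. The participant information is not available, and section 9.1 says that the information given covers the risks of the tests. Only the protocol text can be faulted.
- A reader might want a count of people exposed or harmed, or suppose that the neuropathy group is at particular risk. The protocol gives no prevalence of unrecognised retinopathy and no harm rate, and it defines that group by neuropathy, not by eye status.
- A reader might infer that doing the fundus photo first would clear a subject for the step. Section 4.5 describes imaging without eye drops that assesses the optic nerve and macula. Nothing says that it can rule out proliferative disease.

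**Conclusion.** The point holds as a contradiction and an incomplete safeguard. Section 4.5 recognises a retinal bleeding hazard in the resisted exhalation; section 9.2 says that the test has none. This needs no assumption and stands whatever the timing of the imaging.

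The sequencing concern rests on one inference: that imaging absent from the screening list is done after screening. If it is in fact done first, stating so would answer that part.

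In principle the matter touches every screened person, since all are to have the Vagus test. The practical gap is confined to those whose retinal disease is undocumented at screening, and their number cannot be derived from the protocol. The correction is worth making because it concerns participant safety and risk disclosure and costs little.

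**What to change.** 1. In section 9.2, take the Vagus test out of the entry for examinations without risks, and give it an entry of its own stating the retinal risk that section 4.5 already recognises for the resisted exhalation.

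2. Reconcile the two parts of section 4.5 (Vagus test; OCT and fundus) with sections 9.1 and 9.2, so that the protocol states how retinal status is established before the fourth step and at which visit the planned retinal imaging takes place relative to it. What eye information suffices, and how recent it must be, is a clinical rule for the sponsor's clinicians and is not proposed here.

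The cost is a wording change and perhaps some rescheduling, using examinations and record access already planned. One downside should be weighed. Cardiac autonomic reflex tests help decide group eligibility (inclusion criterion 6 and exclusion criterion 16), so if the fourth step has to wait for eye information, group allocation may come later for some subjects.
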